[Part 2 of 2 of the document. The other parts are not shown.]

The AESIs for this study include the following:

- A thrombotic or embolic event of any severity

All AESIs, whether serious or non-serious, must be reported by the Investigator to the Sponsor immediately (i.e., no more than 24 hours after learning of the event). Non-serious AESIs must be entered on the AE eCRF with a check in the AESI box.

9.2. Methods and Timing for Capturing and Assessing Safety Parameters

The Investigator is responsible for ensuring that all AEs (Section 9.1.1 for definition) are recorded on the AE eCRF and reported to the Sponsor in accordance with instructions provided in this section.

For each AE recorded on the AE eCRF, the Investigator will make an assessment of seriousness (Section 9.1.2), causality (Section 9.2.2), and severity (Section 9.2.3).

9.2.1. Adverse Event Reporting Period

To comply with regulatory requirements, all SAEs and non-serious AESIs, regardless of causality, that occur from the date of signing of the ICF until 30 days after the last study drug treatment, must be reported to Portola or its safety designee within 24 hours from Investigator

awareness of the event. Survival status and reason for death will be ascertained at the Follow-up Day 30 study visit.

Patients who experience an andexanet-related AE or SAE will be followed until the AE or SAE is resolved or until a new stable baseline is established, even if this occurs after the Follow-up Day 30 visit. All AEs spontaneously reported by the patient and/or in response to an open question from study personnel or revealed by observation, physical examination, or other diagnostic procedures will be recorded and reported on the appropriate eCRF through the Follow-up Day 30 visit.

After informed consent has been obtained **but prior to initiation of study drug**, only SAEs caused by a protocol-mandated intervention (e.g., invasive procedures such as biopsies, discontinuation of medications) should be reported to Portola or safety designee. These pre-dose AEs will be collected on the AE eCRF and assessed as not related to study drug, but will be assessed for relationship to study procedures/tests and interventions.

After initiation of study drug, all TEAEs, regardless of relationship to study drug, will be reported until **30 days after the last dose of study drug**. Any SAE that occurs with an onset date later than 30 days after completion of the study and that the Investigator considers to be related to study medication must be reported to Portola or safety designee.

To report any SAEs, the SAE Report Form provided to the clinical study site must be completed with the available information. Non-serious AEs that are AESIs must be reported on the SAE form with the box for AESI checked. The information collected must include at minimum the following: patient number, study drug(s) received, the event term, the serious criteria met for the AE, a narrative description of the event, and an assessment by the Investigator of the severity/intensity of the event and relationship to study drug(s). The SAE report should be sent to Portola or safety designee within 24 hours of Investigator awareness. Follow-up information on the SAE should be sent promptly by the Investigator to Portola or safety designee when any additional relevant information about the SAE becomes known to the Investigator, or as requested by Portola or safety designee. Safety reporting contact information is located in the Study Reference Manual.

Portola will immediately notify the Investigator about important safety or toxicology information, including antibodies against FX or FXa identified in a patient treated with andexanet in any clinical study, as it becomes available. It is the responsibility of the Investigator to promptly notify the Institutional Review Board (IRB)/Independent Ethics Committee (IEC) about new and relevant safety information regarding the study drug, including serious adverse drug reactions involving risk to human subjects, in accordance with the applicable policies. Certain countries (e.g., the Netherlands), require Portola to notify the IRB/IEC about new and relevant safety information regarding the study drug, including serious

adverse drug reactions involving risk to human subjects. An unexpected event is one that is not listed by nature or severity in the Investigator's Brochure.

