11.7. Safety Endpoints and Summaries

Safety will be assessed by examining the following endpoints and analyzed in the Safety Analysis Population:

- AEs (including SAEs), vital signs, physical examinations, and clinical laboratory measurements.
- TEs within 30 days of enrollment, including those suspected and confirmed by adjudication.
- Centrally-adjudicated deaths within 30 days of enrollment, including all-cause mortality and cardiovascular mortality.
- Antibodies to FX, FXa, andexanet, and HCPs.

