4.6. Study Completion

Study completion for each patient is defined as completion of the Day 30 visit or, at a minimum, the time at which Day 30 mortality data are recorded.

In certain European Union Member States, “study completion” may also be considered the same as “end of trial.”

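### Section 9.2.1 gives two incompatible reporting rules before the first dose, and leaves about a month after routine reporting with no dated duty to report a new related SAE

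*Protocol*

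**What the plan says.** Section 9.2.1 of the protocol contains five timing rules. The Amendment 1 text and the original text agree on all of them.

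- **First paragraph:** "all SAEs and non-serious AESIs, regardless of causality, that occur from the date of signing of the ICF" go to the sponsor within 24 hours. The full window is "from the date of signing of the ICF until 30 days after the last study drug treatment".
- **Second paragraph:** all AEs are "recorded and reported on the appropriate eCRF through the Follow-up Day 30 visit".
- **Third paragraph:** after consent but before study drug, "only SAEs caused by a protocol-mandated intervention" are to be reported.
- **Fourth paragraph, TEAEs:** reported until 30 days after the last dose.
- **Fourth paragraph, late events:** the duty covers "Any SAE that occurs with an onset date later than 30 days after completion of the study" if the investigator considers the event related.

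Section 4.6, in the original protocol, states: "Study completion for each patient is defined as completion of the Day 30 visit", or at a minimum the time when Day 30 mortality is recorded. The schedule in Appendix A gives that visit a window of +7 days.

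Section 11.7 lists among the safety endpoints "TEs within 30 days of enrollment, including those suspected and confirmed by adjudication". Section 10.1.8 sets enrollment at consent plus eligibility, and Section 11.3.1 says that it does not depend on receiving andexanet.

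**The concern.** Before dosing, a rule for all events regardless of cause and a rule for events with one cause cannot both apply. Take a myocardial infarction between consent and bolus that no study procedure caused. A site must report it within 24 hours under the first paragraph and is told not to under the third. Section 9.2.4.6 ties the reporting of deaths to the protocol-defined AE period, so it inherits the uncertainty.

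After treatment, the late rule is anchored to study completion rather than to the point where routine reporting stops. The result is out of order: a new related SAE two and a half months after dosing must be reported, but one at six weeks falls under no dated rule. The only antibody sample after baseline is taken at Day 30, so a reaction that followed a positive result could well begin in the uncovered period.

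What is at stake is completeness and consistency of safety reporting, not the efficacy estimate.

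**Working it through.** **Inputs.**
- Routine reporting ends at last dose + 30 days (Section 9.2.1).
- AE recording ends at the Day 30 visit (Section 9.2.1).
- The Day 30 visit falls at 30 to 37 days (Appendix A).
- Completion is that visit (Section 4.6).
- The late rule begins after completion + 30 days (Section 9.2.1).

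**The plan's own figure.** Maximum individual duration is 30 + 7 = 37 days, which matches Section 3.3.

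**Late gap.** Days are counted from dosing as day 0. Gap = (visit day + 30) − end of the preceding window.

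| Case | Preceding window ends | Late rule begins after | Gap |
|---|---|---|---|
| Visit at day 30, single course | 30 | 30 + 30 = 60 | 60 − 30 = 30 days |
| Visit at day 37, single course | 30 | 37 + 30 = 67 | 67 − 30 = 37 days |
| Visit at day 30, re-dose one day later | 31 | 60 | 60 − 31 = 29 days |
| Visit at day 37, re-dose one day later | 31 | 67 | 67 − 31 = 36 days |
| Counted from the visit itself | 30 or 37 | 60 or 67 | 30 days in both |

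If the dosing day is numbered Day 1, as in the schedule, the first four gaps are one day shorter. The 30 days from the visit do not change. If the late rule started at last dose + 30 days, the gap would be 0.

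**Pre-dose rules side by side.** The first paragraph covers the interval from consent onward, all SAEs and AESIs, any cause. The third covers the part of that interval before drug, SAEs only, one cause. Section 9.1.3 requires all AESIs, serious or not, within 24 hours, and Appendix A records AEs from the screening column. Both sit with the first paragraph.

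**Enrollment clock (minor).** Appendix A schedules consent and eligibility at −120 to −45 minutes from surgery and the bolus at −30 to −5 minutes.
- Shortest lag: 45 − 30 = 15 minutes.
- Longest lag: 120 − 5 = 115 minutes, which is 115 / (30 × 24 × 60) = 0.27% of 30 days.
- Outer bound, if surgery starts within 12 hours of consent: about 12 / 720 = 1.7% of 30 days.

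**The case against.** The best defence of the pre-dose text is that the third paragraph is a specific rule qualifying a general one. That would be the natural reading if the first paragraph did not say that cause is irrelevant. AEs are also recorded from screening, so a pre-dose event is not lost from the database. The conflict is confined to reporting to the sponsor over minutes to hours. That limits its size but does not remove it.

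On the late gap, several points stand:

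- The text is silent rather than permissive. A reader might infer that a related SAE in this period is exempt from reporting, but nothing says so.
- Section 9.1.3 requires AESIs to be sent within 24 hours and gives no end date, so thrombotic events may be covered. Other related SAEs are not.
- Section 9.2.1 also has the investigator notify the ethics body of serious adverse drug reactions, without an end date. That is a different recipient.
- Recording through the Day 30 visit covers days 31 to 37 when the visit is late. The gap after it is still 30 days.
- The instruction to follow related events to resolution concerns events already under way, not new onsets.
- The completion definition comes from the original protocol, because Section 4.6 of Amendment 1 is not shown. The summary of changes in Appendix G lists no change to it.

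On the enrollment clock, two stronger readings are tempting and neither is supported. One is that 30-day mortality mixes time before and after exposure. The Safety Analysis Population contains treated patients only (Section 11.3.2), so a death before dosing cannot enter it. The other is that the thrombotic rate cannot be compared with the earlier bleeding study, whose events Section 3.5 dates from treatment. No such comparison is planned in the text shown, so no analysis depends on it. Section 11.7.1 also plans a separate summary of thromboembolic AESIs among treatment-emergent events.

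**Conclusion.** The point holds for two sentences of Section 9.2.1. The pre-dose rules contradict each other. The late rule leaves about 29 to 37 days after the end of post-dose reporting, or exactly 30 days after the Day 30 visit, with no dated obligation to report a new related SAE; thrombotic events are a possible exception.

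The length rests on completion meaning the Day 30 visit, carried over unchanged from the original protocol. Section 4.6 allows completion to be read as end of trial in some EU states; the gap would then be longer for patients enrolled early.

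The enrollment anchor is a minor matter of classification. A thrombotic event after enrollment but before the bolus, in a patient who is then treated, would count toward the endpoint. The effect on 30-day thrombotic rates is negligible, and mortality is unaffected.

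**What to change.** 1. **Pre-dose:** reconcile the first and third paragraphs of Section 9.2.1 into one rule for consent to first dose, consistent with Section 9.1.3 and Appendix A. Flag pre-dose events and tabulate them separately.
2. **Late rule:** replace the anchor, so that the duty applies to any SAE considered related with onset later than 30 days after the last dose of study drug. It then begins where routine reporting ends.
3. **Section 11.7 (minor):** count thrombotic events from the start of andexanet, or keep enrollment and flag pre-dose events.

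The cost is a few sentences in Sections 9.2.1 and 11.7, a matching update to the safety plan, and possibly a few more reports from sites. Sample size, visits and the efficacy analysis do not change.

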9.2.2. Assessment of Causal Relationship

Investigators should use their knowledge of the patient, the circumstances surrounding the event, and an evaluation of any potential alternative causes to determine whether or not an AE is considered to be related to the study drug. The following guidance should be taken into consideration:

- Temporal relationship of event onset to the initiation of study drug.
- Course of the event, considering especially the effects of dose reduction, discontinuation of study drug, or re-introduction of study drug (as applicable).
- Known association of the event with the study drug or with similar treatments.
- Known association of the event with the disease under study.
- Presence of risk factors in the patient or use of concomitant medications known to increase the occurrence of the event.
- Presence of non-treatment-related factors that are known to be associated with the occurrence of the event.

The following categories should be used in the causality assessment of suspected adverse reactions:

Probable

The AE:

- Follows a reasonable temporal sequence from the time of study drug administration; and/or
- Follows a known response pattern to the study drug; and
- Was unlikely to have been produced by other factors, such as the patient's clinical state, therapeutic intervention, or concomitant therapy.

Possible

The AE:

- Follows a reasonable temporal sequence from the time of study drug administration; and/or
- Follows a known response pattern to the study drug; but
- Could have been produced by other factors, such as the patient's clinical state, therapeutic intervention, or concomitant therapy.

Unlikely

The AE:

- Does not follow a reasonable temporal sequence from the time of study drug administration; and
- Was most likely produced by other factors, such as the patient's clinical state, therapeutic intervention, or concomitant therapy.

Unrelated

- This category is applicable to those AEs that are judged to be clearly and incontrovertibly due only to extraneous causes (e.g., the patient's clinical state, therapeutic intervention other than bleeding control, or concomitant therapy) and do not meet the criteria for study drug relationship listed under Probable, Possible, or Unlikely.

An AE with causal relationship not initially determined will require follow-up to assign causality. Importantly, lack of efficacy does not necessarily constitute relatedness to study drug.

9.2.3. Assessment of Severity

The Investigator must determine the severity of the event according to the criteria below and the Investigator's clinical judgment. Severity describes the intensity of the AE.

Grade 1	Mild; asymptomatic or mild symptoms; clinical or diagnostic observations only; or intervention not indicated
Grade 2	Moderate; minimal, local, or non-invasive intervention indicated; or limiting age-appropriate instrumental activities of daily living
Grade 3	Severe or medically significant, but not immediately life-threatening; hospitalization or prolongation of hospitalization indicated; disabling; or limiting self-care activities of daily living
Grade 4	Life-threatening consequence or urgent intervention indicated
Grade 5	Event resulted in death

9.2.4. Procedures for Recording AEs

Investigators should use correct medical terminology/concepts when recording AEs on the AE eCRF. Avoid colloquialisms and abbreviations. Only 1 AE term should be recorded in the event field on the AE eCRF.

All AEs spontaneously reported by the patient and/or in response to an open-ended question from study personnel or revealed by observation, physical examination or other diagnostic procedures will be recorded on the appropriate forms in the eCRF.

Only 1 AE term should be recorded in the event field on the AE eCRF. When possible, a unifying diagnosis, or signs and symptoms indicating a common underlying pathology should be noted as 1 comprehensive event. For example, the combination of general malaise, mild fever, headache, and rhinitis should be described as a “common cold” rather than listing each symptom separately.

9.2.4.1. Diagnosis versus Signs and Symptoms

A diagnosis (if known) should be recorded on the AE eCRF rather than individual signs and symptoms (e.g., record only liver failure or hepatitis rather than jaundice, asterixis, and elevated transaminases; record tumor lysis syndrome rather than hypocalcemia, hyperkalemia, hyperuricemia, etc.). However, if a constellation of signs and/or symptoms cannot be medically characterized as a single diagnosis or syndrome at the time of reporting, each individual event should be recorded on the AE eCRF. If a diagnosis is subsequently established, all previously reported AEs based on signs and symptoms should be nullified and replaced by 1 AE report based on the single diagnosis, with a starting date that corresponds to the starting date of the first symptom of the eventual diagnosis.

9.2.4.2. Adverse Events that are Secondary to Other Events

In general, AEs that are secondary to other events (e.g., cascade events or clinical sequelae) should be identified by their primary cause, with the exception of severe or serious secondary events. A medically significant secondary AE that is separated in time from the initiating event should be recorded as an independent event on the AE eCRF. For example:

- If vomiting results in mild dehydration with no additional treatment in a healthy adult, only vomiting should be reported on the eCRF.
- If vomiting results in severe dehydration, both events should be reported separately on the eCRF.
- If a severe gastrointestinal hemorrhage leads to renal failure, both events should be reported separately on the eCRF.
- If dizziness leads to a fall and consequent fracture, all 3 events should be reported separately on the eCRF.
- If neutropenia is accompanied by an infection, both events should be reported separately on the eCRF.

All AEs should be recorded separately on the AE eCRF if it is unclear as to whether the events are associated.

9.2.4.3. Persistent or Recurrent Adverse Events

A persistent AE is one that extends continuously, without resolution, between patient evaluation time points. Such events should only be recorded once on the AE eCRF with the severity (intensity or grade) of the events recorded at the time the event is first reported.

A recurrent AE is one that resolves between patient evaluation time points and subsequently recurs, or notes a change in severity or seriousness. Each recurrence of an AE should be recorded as a separate event on the AE eCRF. For example:

- If Grade 1 vomiting has worsened to Grade 2 five days after onset, the Grade 1 vomiting is resolved on the date when the severity changed, and Grade 2 vomiting is recorded as a new event on the eCRF with onset date reflecting the change in severity.

If non-serious event of neutropenia required hospitalization 5 days after onset, the event is resolved on the hospitalization date, and a new SAE of neutropenia is recorded on the eCRF with start date reflecting when the event required hospitalization

9.2.4.4. Abnormal Laboratory Values

Not every laboratory abnormality qualifies as an AE. A laboratory test result must be reported as an AE if it meets any of the following criteria:

- Is accompanied by clinical symptoms
- Results in a change in study treatment (e.g., dosage modification, treatment interruption, or treatment discontinuation)
- Results in a medical intervention (e.g., potassium supplementation for hypokalemia) or a change in concomitant therapy
- Is clinically significant in the Investigator's judgment

It is the Investigator's responsibility to review all laboratory findings. Medical and scientific judgment should be exercised in deciding whether an isolated laboratory abnormality should be classified as an AE.

If a clinically significant laboratory abnormality is a sign of a disease or syndrome (e.g., alkaline phosphatase and bilirubin $5 \times$ upper limit of normal [ULN] associated with cholestasis), only the diagnosis (i.e., cholestasis) should be recorded on the AE eCRF.

9.2.4.5. Abnormal Vital Sign Values

Not every vital sign abnormality qualifies as an AE. A vital sign result must be reported as an AE if it meets any of the following criteria:

- Is accompanied by clinical symptoms.

- Results in a change in study treatment (e.g., dosage modification, treatment interruption, or treatment discontinuation).
- Results in a medical intervention or a change in concomitant therapy.
- Is clinically significant in the Investigator's judgment.

It is the Investigator's responsibility to review all vital sign findings. Medical and scientific judgment should be exercised in deciding whether an isolated vital sign abnormality should be classified as an AE.

If a clinically significant vital sign abnormality is a sign of a disease or syndrome (e.g., high blood pressure), only the diagnosis (i.e., hypertension) should be recorded on the AE eCRF.

Observations of the same clinically significant vital sign abnormality from visit to visit should only be recorded once on the AE eCRF (Section [9.2.4.3](#) provides details on recording persistent AEs).

9.2.4.6. Deaths

Death should be considered an outcome and not a distinct event. All deaths that occur during the protocol-defined AE period should be reported as SAEs, regardless of attribution to study drug. The event or condition that caused or contributed to the fatal outcome should be recorded as the single medical concept (e.g., septic shock) with a fatal outcome. When the event that led to death cannot be identified (e.g., death of unknown origin) report "unexplained death" as the AE and update it when new information clarifies the event that led to death. Only 1 AE can be reported with a fatal outcome for each patient who dies. Other AEs that continued up to time of death should be reported with an outcome of not recovered/resolved. In the event that the death is attributed solely to natural progression of the underlying bleeding, the event is not reportable and should not be recorded as an AE.

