10.5. End of Study Assessments

Patients will have their survival status reported on the Day 30 or End of Study visit. This assessment will record the patient's status as alive or provide the date, time and cause of death. Note: see Section 9.0 for AEs reported for all deaths.

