11.7.3. Deaths

All deaths will be assessed by the EAC. Deaths due to cardiovascular causes (i.e., resulting from MI, sudden cardiac death, heart failure, stroke, cardiovascular procedures, cardiovascular hemorrhage, and other cardiovascular causes) will be classified as related to bleeding or non-hemorrhagic.

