4.2. Exclusion Criteria

If a patient meets any of the following criteria, he or she is *not* eligible to participate:

1. Surgery predicted to last > 4 hours or for which the risk of clinically meaningful uncontrolled or unmanageable bleeding is low.
2. Acute life-threatening bleeding at the time of Screening.
3. Any surgical procedure requiring cardiopulmonary bypass, an intra-aortic catheter, or the intra-operative use of systemic, intravascular, unfractionated heparin.
4. Expected survival of < 1 month due to comorbidity.
5. Existing “Do Not Resuscitate” order or similar advanced directive.
6. The patient has a recent history (within 30 days prior to Screening) of a diagnosed TE as follows: VTE (including DVT, PE, intracardiac thrombus); myocardial infarction (including asymptomatic troponin elevations); disseminated intravascular coagulation (DIC); acute traumatic coagulopathy; cerebrovascular accident; transient ischemic attack; unstable angina pectoris hospitalization; or severe peripheral vascular disease (see [Appendix B](#) for DIC scoring algorithm).
7. Acute decompensated heart failure or cardiogenic shock at the time of screening (see [Appendix C](#) for cardiogenic shock definition)

8. The patient has severe sepsis or septic or hemorrhagic shock at the time of Screening (see definition in [Appendix C](#)).
9. The patient is pregnant or a lactating female.
10. The patient has received any of the following drugs or blood products within 7 days of enrollment:
 - VKA (e.g., warfarin).
 - Dabigatran.
 - Prothrombin complex concentrate products (PCC, e.g., Kcentra[®]), recombinant factor VIIa (rfVIIa) (e.g., NovoSeven[®]).
 - Whole blood, plasma fractions.
 - Note: Administration of tranexamic acid (TXA), platelets, or packed red blood cells (PRBCs) is not an exclusion criterion.
11. The patient was treated with an investigational drug < 30 days prior to Screening.
12. Prior treatment with andexanet.

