9.1.2. Serious Adverse Events

An SAE is any AE, occurring at any dose and regardless of causality, that:

- Is fatal (i.e., the AE actually causes or leads to death).
- Is life-threatening. Life-threatening means that, in the opinion of the Investigator or Study Sponsor, the patient/subject was at immediate risk of death from the reaction as it occurred, (i.e., it does not include a reaction that hypothetically might have caused death had it occurred in a more severe form).
- Requires inpatient hospitalization or prolongation of existing hospitalization.
- Results in persistent or significant disability/incapacity. Disability is defined as a substantial disruption of a person's ability to conduct normal life functions.

- Is a congenital anomaly/birth defect in a neonate/infant born to a mother who was exposed to study drug or where the father was exposed to study drug before conception.
- Is an important medical event. An important medical event is an event that may jeopardize the patient/subject and may require medical or surgical intervention to prevent one of the outcomes listed in the definitions for SAEs above. Examples of such medical events include allergic bronchospasm requiring intensive treatment in an emergency room or at home, blood dyscrasias or convulsions that do not result in inpatient hospitalization, or the development of drug dependency or drug abuse.

A distinction should be made between the terms “serious” and “severe” since they **are not** synonymous. The term “severe” is often used to describe the intensity (severity) of a specific event (as in mild, moderate, or severe myocardial infarction); the event itself, however, may be of relatively minor medical significance (such as severe headache). This is **not** the same as “serious,” which is based on the strict regulatory definitions listed above and serves as a guide for defining regulatory reporting obligations. A severe AE does not necessarily need to be considered serious. For example, persistent nausea of several hours duration may be considered severe nausea but not an SAE if the event does not meet the serious criteria. On the other hand, a stroke resulting in only a minor degree of disability may be considered mild but would be defined as an SAE based on the above noted serious criteria. Thus, severity and seriousness need to be independently assessed for each AE recorded on the AE electronic Case Report Form (eCRF).

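### Section 9.2.4.6 makes every death an SAE and then exempts deaths from an undefined underlying bleeding, so fatal SAEs could be fewer than adjudicated deaths

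*Protocol*

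**What the plan says.** Section 9.2.4.6 (Deaths) opens with a general rule: "All deaths that occur during the protocol-defined AE period should be reported as SAEs, regardless of attribution to study drug". Its last sentence takes one class of death out: where the "death is attributed solely to natural progression of the underlying bleeding, the event is not reportable and should not be recorded as an AE". The same sentence stands in the original 2019 protocol contained in the same file, so Amendment 1 kept it.

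Three other places bear on it:

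- Section 9.2.1 requires 24-hour reporting of "all SAEs and non-serious AESIs, regardless of causality, that occur from the date of signing of the ICF until 30 days", counted from the final andexanet treatment. Its rule for TEAEs begins "After initiation of study drug, all TEAEs, regardless of relationship to study drug, will be reported until" and sets a limit of the same length.
- Section 10.5 records survival status and cause of death at Day 30, with the note "see Section 9.0 for AEs reported for all deaths".
- Section 9.1.2, seen here only in the original protocol, lists as its first criterion for an SAE: "Is fatal (i.e., the AE actually causes or leads to death").

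On the population, Section 4.2 of the original protocol excludes "Acute life-threatening bleeding at the time of Screening". The Amendment 1 eligibility section is not in the text shown, but the change log in Appendix G shows this exclusion kept and expanded with ISTH criteria.

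**The concern.** An exemption for death from the underlying disease fits a trial that enrols patients because they are bleeding. This trial enrols patients because they need urgent surgery, and it screens out those with life-threatening bleeding. The protocol text shown does not say which bleeding counts as underlying. The investigator, who knows the treatment, makes the attribution.

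At stake is the AE and SAE record. A fatal bleed around surgery is an outcome of obvious interest for a reversal agent. If it is placed under the exemption, the sponsor gets no expedited report and the event is absent from the AE tables. The omission can only lower the count of fatal SAEs, and a single-arm study has no control group in which the same loss would show.

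**Working it through.** No figure in the plan depends on this rule, so there is nothing to recompute. The check is a comparison of the passages.

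**1. Within Section 9.2.4.6.** The opening rule covers all deaths and sets attribution to study drug aside. The closing sentence makes reporting depend on attribution to a bleed. For a death in the exempt class, one sentence requires an SAE report and the other forbids it.

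**2. Against Section 9.2.1.** After dosing starts, SAEs and TEAEs are reported whatever their cause or relationship. Section 9.2.1 has a narrower rule between consent and first dose, so the comparison is confined to deaths after dosing. There it contains no exception for bleeding.

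**3. Against Section 10.5.** Its note presumes that Section 9.0 yields an AE for every death. Under the exemption it does not.

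**4. Against Sections 9.2.4.2 and 9.2.4.7.** The first uses severe gastrointestinal hemorrhage as an example of a recordable event. The second makes a preexisting condition an AE if it worsens. A bleed present at entry that worsens without killing is therefore recorded, while the same bleed that kills is not.

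**5. What the exemption can cover.** If *underlying* means a bleed present at entry, the exclusion of acute life-threatening bleeding leaves few patients to whom it could apply. If sites read it more widely, it can take in a bleed that begins during or after surgery. The text shown does not settle which reading is meant.

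**6. Consequence for the outputs.** Let D be the deaths in the AE period and k the number placed under the exemption. Then:

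- fatal SAEs = D − k;
- deaths assessed by the EAC under Section 11.7.3 = D, because that section takes all deaths;
- shortfall = D − (D − k) = k, which is zero or positive and never negative.

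The mortality endpoint in Section 11.7 counts from enrollment and the AE period runs from the last dose. The two windows nearly coincide because treatment takes place around surgery.

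Section 13.4 reconciles SAEs between the clinical and safety databases. A death entered as an SAE in neither would not appear there as an SAE discrepancy.

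**The case against.** The strongest reply is that the exemption is narrow. It needs a death attributed *solely* to the *natural progression* of an *underlying* bleed, and on a plain reading a new intraoperative or postoperative bleed is none of these. That stands as far as it goes. A reader might infer that fatal bleeds in general drop out of safety reporting; the wording does not say so. What remains is an undefined term, applied by the site, in a paragraph that also states the opposite rule.

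The second reply is that deaths are captured elsewhere, and this also stands. Section 11.7 lists centrally adjudicated 30-day deaths as a safety endpoint. Section 11.7.3 sends all deaths to the EAC. Section 11.7.1 sends all potential post-surgical bleeding events there, and Section 12.0 has the DSMB monitor all safety data. A reader might infer that an exempt death would surface only through Day 30 survival status, or that the DSMB could not learn of it. The documents support neither. These routes do not, however, replace the 24-hour report or put the event back in the TEAE tables.

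Third, a reader might call a fatal bleed the trial's main treatment failure and conclude that the efficacy result is biased. Section 11.5.2.1 defines failure as Moderate or Poor intraoperative hemostasis, which does not use AE records. Neither the primary endpoint nor all-cause mortality is affected.

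Fourth, Section 11.7.3 says that cardiovascular deaths "will be classified as related to bleeding or non-hemorrhagic". A reader might infer that a fatal surgical-site bleed judged non-cardiovascular is never labelled a bleeding death. That is not established: cardiovascular hemorrhage is among the listed causes, and the EAC Charter, which may settle the matter, is not shown.

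**Conclusion.** The contradiction is real and stands in the current text. Section 9.2.4.6 conflicts with itself, with Section 9.2.1 and with Section 10.5. Followed literally, its last sentence removes a death from expedited SAE reporting and from the TEAE and serious TEAE tables, while leaving it in adjudicated mortality. Fatal SAEs could therefore be fewer than adjudicated deaths, and the gap can run in only one direction.

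The size cannot be estimated. It might be tempting to carry over the 30-day mortality of the earlier study in bleeding patients given in Section 1.4.7 (54/352 = 15.3%) and take a share of it. That study enrolled patients with acute major bleeding, 64% of them intracranial, a population this trial largely excludes. The documents give no share of deaths due to bleeding, and not every bleeding death would meet the terms of the exemption. The number is probably small, and may be zero if sites read the terms strictly.

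The conclusion assumes that no definition of underlying bleeding stands in the part of Amendment 1 not shown, and that its eligibility section matches the change log.

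**What to change.** Delete the last sentence of Section 9.2.4.6, so that every death in the AE period is reported as an SAE under the term for its cause; the section already provides a term for unexplained death. Then read Sections 9.2.1, 9.2.4.6 and 10.5 together and make them agree, stating also how the narrower pre-dose rule in Section 9.2.1 applies to a death between consent and first dose.

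Optionally, change Section 11.7.3 so that the EAC classifies every death, cardiovascular or not, as bleeding-related or not. This would let the mortality table answer the bleeding question without relying on how the cardiovascular category is drawn.

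The cost is one deleted sentence, one optional changed sentence, a memo to sites and possibly a few more SAE forms. If patients have already been followed under the current text, compare the list of adjudicated deaths with the fatal SAEs and complete any missing reports.
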